11.4 Cost-of-illness (COI)

The objective of this COI analysis is to calculate the societal costs of MICCH in the Netherlands. This prevalence based, retrospectively and bottom-up cost of illness study will be performed at baseline. Data for this COI will come from the baseline measurements of the a cost questionnaire especially designed for this group, based on existing questionnaires, which will identify all relevant costs aspects (33;34). The valuation of the COI will be based on the same methods as used in the economic evaluation (37).

12. Protocol deviations

Investigators are required to adhere to the Investigational Plan, signed Investigator's Agreement, applicable national or local, laws and regulations, and any conditions required by the appropriate Ethics Committees (EC) or applicable regulatory authorities.

Deviations from the protocol will not be permitted, except where necessary to protect the life or physical well-being of a patient in an emergency situation. If circumstances permit, the investigator should inform study management before initiating deviations. Prior notification is generally not expected in situations where unforeseen circumstances are beyond the investigator's control (e.g. patient did not attend scheduled follow-up visit). The investigator is required to adhere to the EC procedures for reporting deviations. Deviations include, but are not limited to the following:

- Failure to obtain informed consent prior to patient enrolment •
- Incorrect version of the informed consent form used •
- Enrolled patient did not meet the inclusion/exclusion criteria ٠
- Adverse Events not reported by investigators in the required timeframe as • specified in the protocol

Centre compliance with regard to deviations will be reviewed by the study coordinator on a timely basis. In addition, all deviations from the CIP will be documented in the final report.

13. Safety monitoring

The study investigators are responsible for the detection and documentation of adverse events (AEs) and device events.

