A similar design was successfully used in a multicenter, prospectively randomised, parallel, double-blind study that showed that high vagus nerve stimulation gave significantly more reduction in seizure frequency than low vagus nerve stimulation (24). This finding supports a proposed dose response in neurostimulation and subsequently supports our design. Supposed treatment allocation by the patient, on the other hand, was not mentioned in this study.

Matharu et al. (25) showed a correlation between mean pain scores, stimulator induced paresthesia and changes in regional cerebral blood flow in ONS treated chronic migraine patients. These findings suggest a dose related effect of the stimulation and thereby supports our design.

Blinding

Patients, neurologists and the study investigator will be blinded for the randomisation. The IPG programming (not blinded) will be performed by the implanter (neurosurgeon or anaesthesiologist) or research nurse. They will take precautions to ensure that patients are unaware of their randomisation status by not informing them about the stimulation conditions.

Protocol: Occipital nerve stimulation in medically intractable, chronic cluster headache CME Protocol number: 10.016

Follow-up

Follow-up second period

			V	'ersio	n 1.1	1 dd. 26	5-09-2	2018			I														
T=6	12 months	after	surgery		+ 4	weeks							X		X						X		X		
T=5	9 months	after	surgery		± 4	weeks							Х		Х								Х		
T=4	6 months	after	surgery		± 2	weeks							Х		X			Х			Х		Х		
T=3	4 months	after	surgery		± 2	weeks							Х		Х								Х		
T=2	2 months	after	surgery		± 1 week								Х		Х								Х		
T=1	1 month	after	surgery		± 1 week								Х		Х								Х		
T=0	10 days	after	surgery		± 2 days						Х				Х								Х		
T=-1	Interventio	n								X	X				Х								X		
T=-2	Pre-op 3	months	after	inclusion									Х					Х					Х		
T=-3	Inclusion	start	electronic	diary			Х						Х										Х		
					Visit	Window	Patient	characteristi	cs	Intervention	Wound	inspection	Headache	diary	Stimulation	and system	check	Economic	evaluation	questionnaire	Patient	satisfaction	Adverse	events	

5. Patient recruitment

Patients will be recruited from tertiary headache clinics in The Netherlands, Denmark,

UK and probably Belgium and Germany.

6. Study Purpose

Objectives

The primary objective of this study is to investigate whether ONS reduces the attack frequency in MICCH compared to baseline.

7. Endpoints

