8.1 Inclusion Criteria

- ICHD-II criteria for CCH (see above)
- Minimum mean attack frequency of 4 attacks per week
- Minimum age of 18 years old
- Signed study specific informed consent form agreeing to implantation of the device, data collection and follow-up requirements
- Agreeing to refrain from starting new prophylactic CH medication, including steroids, or any other therapy aimed at CH (such as acupuncture, biofeedback, chiropractic, or massage) and agrees to maintain existing prophylactic CH medication from 4 weeks before entering the baseline

period throughout the duration of the double blind phase of the study. It is allowed to change the dose of prophylactic medication during the study based on the opinion of the treating medical specialist.

- Availability during follow-up period
- An MRI not older than 4 years prior to enrolment must be available to exclude structural lesions potentially causing CCH. An exception can be realized by the study coordinator in case of stable CH for over 4 years and no change in symptoms after the last MRI scan was performed.
- MRA of head and neck are to be performed according to study physician's individual judgement.
- Medically intractable (see below)

Definition medically intractable :(2)

Failed adequate trials of regulatory approved and conventional treatments according to local national guidelines

Current prophylactic treatment of CH consists of corticosteroids (short term only), methysergide (short term only), verapamil and lithium. Other drugs, such as valproate, pizotifen, topiramate and gabapentin are also used without clinical evidence (27). Prolonged treatment with methysergide has been associated with fibrotic reactions and therefore is no longer available in the USA and some other European countries. Corticosteroids are often efficacious, but treatment should be limited to 6-8 weeks. For this reason patients do not have to be intractable for corticosteroids to be included in the study. Verapamil is the preventive drug of choice in CCH, followed by lithium (28).

Adequate trial:

Appropriate dose and duration of treatment according to local guidelines Appropriate length of time Consideration of medication overuse

Failed:

No therapeutic or unsatisfactory effect, intolerable side effects, contraindications to use

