9.2 Schedule

Visit 1: study neurologist: inclusion/exclusion criteria

Visit 2: visit neurosurgeon (or implanter)/investigator: information about the surgery and study: reflection period of 7-14 days (or as long the patients needs)

Visit 3: informed consent study neurologist. Start electronic diary

Visit 4: anaesthesiologist

Evaluation headache diary by study coordinator: does the patient still meet inclusion criteria: at least 4 attacks per week?

Interview by telephone (medical student): economic evaluation questionnaire

Randomisation

Visit 5: surgery and defining stimulation parameters: 2-3 days in hospital

Visit 6: **+10 days** control of wound and removal of stitches **t=0** and calibration of stimulation

Visit 7: + 1 month: checking and changing of stimulation follow-up

Visit 8: + 2 months checking and changing of stimulation follow-up

Visit 9: + 4 months: checking of stimulation follow-up

Interview by telephone (student) after 6 months: economic evaluation questionnaire

Visit 10: + 6 months: checking of stimulation follow-up

Plus monthly visits study neurologist (an exception will be made for the visits at 3 and 5 months follow-up, because in case the participating patient prefers a telephone call instead, this will be allowed)

Open trial:

Visit 11: +9 months: checking of stimulation follow-up

Visit 12: + 12 months: checking of stimulation follow-up

Plus three-monthly visit study neurologist

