11.1 Design and participants

Economic evaluations compare additional costs and additional outcomes of high stimulation compared to low stimulation. This economic evaluation will involve a combination of a cost-effectiveness analysis (CEA) and a cost-utility analysis (CUA). In a CEA effects are presented in clinical outcomes (in our study frequency of CH attacks during the last 4 weeks of the 100% stimulation period and the 30% stimulation period). The primary outcome measure for the cost-utility analysis will be Quality Adjusted Life Years (QALYs), based on the SF-36 utility scores (29-31). In the CUA, the Incremental cost-effectiveness ratio (ICER) will be expressed as the incremental costs per QALY. This economic evaluation will be performed from a societal perspective, which implies that all relevant costs and outcomes will be taken into account. With regard to this research question we hypothesize that the high stimulation is associated with an increased effect, and an increase in quality of life. The time horizon will be the same period as the follow-up period of the double blind part of the main study, 6 months. Costs (the use of resources) will be measured continuously using a (retrospective) questionnaire (6 months); outcomes for the economic evaluation study will be measured at pre-test before random assignment into groups (baseline), and at 6 months.

The second part of this economic evaluation will be a cost-of-illness (COI) study. The objective of this COI analysis is to calculate the societal costs of MICCH in the Netherlands. This prevalence based, retrospectively and bottom-up cost of illness Protocol: Occipital nerve stimulation in medically intractable, chronic cluster headache CME Protocol number: 10.016 Version 1.11 dd. 26-09-2018 study will be performed at baseline using a (retrospective) questionnaire (6 months) and an electronic diary for the use of attack medication.

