11.2 Measurement

Cost measures

Total costs will be estimated using a bottom-up (or micro-costing) approach, where information on each element of service used is multiplied by an appropriate unit cost and summed to provide an overall total cost (32). We will assess intervention costs, healthcare costs, patient and family costs, and costs outside the health care sector. For this study we developed a cost questionnaire especially designed for this group, based on existing questionnaires, which will identify all relevant costs aspects (33;34).

To measure the actual use of resources data will be obtained using combined sources (registrations by professionals and cost questionnaire). Resources used relating to the interventions will be based on the registered time all professionals spent on the treatment. Intervention costs will include all the costs that will contribute to the procedure of ONS. All use of resources by the patient and their family in and outside the health care sector, will be measured by means of an interview by telephone, in which they are being asked about volumes of resource utilization 6 months retrospectively at baseline and at 6 months follow up. Cluster headache medication use will be registered in the electronic diary. These 2 sources of information will be combined.

The valuation of healthcare costs, patient and family costs will be based on the updated Dutch manual for cost analysis in healthcare research (35;36). This manual recommends using standardized cost prices. In brief, the manual recommends that prices of informal care will be based on shadow prices for unpaid work (meaning a standard cost price based on general hourly wages). Costs of medication will be calculated using prices taken from the Dutch Pharmacotherapeutic Compass (37). Productivity costs will be calculated by means of the friction cost method, based on a mean added value of the Dutch working population. The friction costs method takes into account production losses confined to the period needed (usually 90 days) to replace a sick employee. In case of uncertainty we will use a conservative estimation

Protocol: Occipital nerve stimulation in medically intractable, chronic cluster headache CME Protocol number: 10.016 Version 1.11 dd. 26-09-2018 (i.e. the lowest cost price). Cost prices will be expressed in 2009 euro's. If necessary, existing cost-prices will be updated to 2011 using the consumer price index (CPI) (35;36).

Outcome measures

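### The Dutch cost-of-illness estimate has no stated country population, and about half of its 6-month recall overlaps the trial baseline with no rule to exclude contacts made for the trial

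*Combined protocol and SAP*

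**What the plan says.** The target is national. Section 11.4: "The objective of this COI analysis is to calculate the societal costs of MICCH in the Netherlands".

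The source is the trial's own baseline interview. Section 11.4: "Data for this COI will come from the baseline measurements of the a cost questionnaire especially designed for this group". Section 11.1 adds the recall length and the diary: "study will be performed at baseline using a (retrospective) questionnaire (6 months) and an electronic diary for the use of attack medication".

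Section 11.2 describes the telephone interview, "in which they are being asked about volumes of resource utilization 6 months retrospectively at baseline and at 6 months follow up". Its scope is all resource use by the patient and family, inside and outside health care. Volumes are multiplied by unit costs, mainly from the Dutch costing manual and the Dutch medicines price list.

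On timing, section 9.2 lists "Interview by telephone (medical student): economic evaluation questionnaire" after the anaesthesiologist visit and the diary evaluation, immediately before randomisation. The visit table in section 4 agrees, marking the questionnaire at T=-2, the pre-operative point 3 months after inclusion.

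On treatment, section 8.1 requires "Agreeing to refrain from starting new prophylactic CH medication, including steroids, or any other therapy aimed at CH", with existing prophylaxis maintained from 4 weeks before baseline. Dose changes are allowed.

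On the sample, section 5 states: "Patients will be recruited from tertiary headache clinics in The Netherlands, Denmark". The sentence goes on to the UK and, probably, Belgium and Germany.

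**The concern.** A cost-of-illness figure should describe what the disease costs society in ordinary care. Three features of the plan pull away from that.

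- **Trial contacts.** The recall reaches back over the weeks in which the patient was being assessed for an experimental implant. Visits to the study neurologist, implanter and anaesthesiologist, pre-operative screening and an MRI done for eligibility are uses of resources, so the scope in section 11.2 would count them.
- **Restricted therapy.** Over much of the same window the patient has agreed to start nothing new for cluster headache. Section 8.1 notes that corticosteroids often work and does not require patients to be intractable to them, so some care used in practice may be missing.
- **Country.** Nothing in section 11.4 stops Danish, UK, Belgian or German volumes from being priced in Dutch units and reported as Dutch costs.

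The first feature pushes the total up and the second may push it down. The effect of the third is unknown. At stake is the interpretability of one named objective.

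**Working it through.** The plan gives no cost-of-illness figure to reproduce. The check is how much of the recall window falls in each period.

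**Inputs**
- Recall length: 6 months (sections 11.1 and 11.2). Section 7.1 defines a month as 4 weeks, giving 6 × 4 = 24 weeks; calendar months give about 26.
- Baseline diary: 12 weeks (section 9.1).
- Restriction on new therapy: starts 4 weeks before baseline (section 8.1). I read the 4-week lead-in as covering new therapy as well as existing prophylaxis. The sentence could be read more narrowly.
- Interview: at the end of baseline (section 9.2; visit table in section 4).

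**Share of recall inside the trial baseline** = 12 / recall weeks
- 12/24 = 50%
- 12/26 = 46%

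**Share under the restriction on new therapy** = (12 + 4) / recall weeks
- 16/24 = 67%
- 16/26 = 62%

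**Weeks before any restriction** = recall weeks − 16
- 24 − 16 = 8
- 26 − 16 = 10

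**If the interview slips by 4 weeks** (an assumption, for sensitivity)
- In trial: 16/24 = 67% or 16/26 = 62%
- Restricted: 20/24 = 83% or 20/26 = 77%

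**Which trial contacts fall in the window.** Consent (visit 3) starts the diary, so it lies 12 weeks before the interview. The anaesthesiologist visit (visit 4) falls between the two. The study neurologist (visit 1) and implanter (visit 2) come before consent, separated from it by a reflection period of 7–14 days or as long as the patient needs. The window extends 24 − 12 = 12 weeks (or 26 − 12 = 14) before consent, so these two visits will normally be inside it as well. Section 9.1 adds pre-operative screening and an MRI where no recent one exists.

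**Whether anything removes them.** Sections 11.1, 11.2 and 11.4 contain no exclusion for trial-driven use. Section 11.2 has a separate category for intervention costs, based on time registered by professionals. That describes the cost of the stimulation procedure and does not say what is left out of the cost-of-illness total.

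**Whether the population is defined.** Sections 11.1 and 11.4 name the Netherlands as the target, and neither says which patients contribute. The share of non-Dutch patients is not given.

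**The case against.** The strongest reply is that the plan is workable as it stands. Costing is bottom-up, so individual items can be identified; trial contacts are few and scheduled, and an analyst could subtract them. The Dutch objective, Dutch prices and Dutch SF-36 all fit a Dutch-only subset. The cost questionnaire is not reproduced and may already tell patients to leave out study visits. The analysis is descriptive and unpowered.

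Much of this stands, and it rules out several stronger readings that a reader might infer:

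- **That the plan pools countries.** It does not say so. The reference in section 11.3 to all participants concerns the intention-to-treat comparison of arms. The gap is an undefined population.
- **That treatment is frozen.** Dose changes are allowed, acute treatment is not restricted by the criteria, and 8 to 10 weeks of the window precede the restriction. Patients have already tried at least three preventive classes, so how much new treatment is displaced is unknown.
- **That the figure measures trial care instead of usual care.** About half of the window precedes inclusion, and the other half still contains ordinary care and lost work.
- **That the contamination is irrecoverable.** Itemised costing contradicts this, provided that the questionnaire separates trial contacts from others.
- **That the interview should move to inclusion.** This would remove the in-trial overlap but still leave 4/24 = 17% (4/26 = 15%) under restriction. It would also lose the overlap with the diary that supplies attack-medication use, and leave about 12 weeks before randomisation outside the baseline recall.

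What the reply does not answer is that subtraction and a Dutch subset are possible but not specified. The written scope points the other way on trial contacts.

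**Conclusion.** The point holds in limited form. Section 11.4 leaves the contributing population undefined and gives no rule for trial-driven contacts, while 46–50% of the recall lies inside the trial baseline and 62–67% under the restriction on new therapy.

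These are shares of time and not of cost. The documents give no resource-use or cost figures, so neither the size nor the net direction of the bias can be stated. The shares assume an interview at the end of a 12-week baseline and the reading of section 8.1 given above; a later interview raises them.

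Severity is low. The primary endpoint, the comparison between arms, the sample size and the safety assessment are unaffected.

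**What to change.** In section 11.4, add:

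1. The cost-of-illness estimate uses patients from Dutch sites only; results from other countries, if shown, are reported separately.
2. Screening and pre-operative contacts made for the trial are recorded separately in the baseline interview and excluded from the cost-of-illness total. If the questionnaire already does this, say so.
3. The restriction on new therapy during the recall window is reported as a limitation.

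Keep the baseline and month-6 interviews at their present times.

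The cost is a few sentences, an added item in the baseline interview if it is not already there, and a smaller cost-of-illness sample whose size the documents do not allow to be stated. The country restriction needs no new data and can be applied after enrolment. For patients already interviewed, trial contacts can be removed only if the questionnaire recorded them by type or date.

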13.1 Adverse Event Definitions

Definition/classification

For the purposes of the clinical report, each adverse event will be classified according to EN ISO 14155-1.

Where the definition indicates "device", it refers to any device used in the study. This might be the device under investigation, or any market released component of the system.

13.2 Adverse Event (AE):

Any untoward medical occurrence in a subject.

NOTE 1: This definition does not imply that there is a relationship between the adverse event and the device under investigation.

13.3 Adverse Device Effect (ADE):

Any untoward and unintended response to a medical device.

NOTE 1: This definition includes any event resulting from insufficiencies or inadequacies in the instructions for use or the deployment of the device.

NOTE 2: This definition includes any event that is a result of a user error.

NOTE 3: This definition includes patients and users.

13.4 Serious Adverse Event (SAE):

An adverse event that

- a) led to death
- b) led to a serious deterioration in the health of a subject that
 - 1) resulted in a life-threatening illness or injury,

2) resulted in a permanent impairment of a body structure or a body function,

3) required in-patient hospitalization (except for the implantation) or prolongation of existing hospitalization, or

4) resulted in medical or surgical intervention to prevent permanent impairment to body structure or a body function

c) led to fetal distress, fetal death or a congenital abnormality or birth defect.

Explanatory note: an Adverse Event is considered Serious if condition 1, 2, 3, or 4 apply in combination with a serious deterioration in health. E.g. a planned hospitalization for a pre-existing condition, without a serious deterioration in health is not considered to be a SAE.

13.5 Serious Adverse Device Effect (SADE):

An ADE that has resulted in any of the consequences characteristic of a Serious Adverse Event or that might have led to any of these consequences if suitable action had not been taken or intervention had not been made or if circumstances had been less opportune. *NOTE:* the definition of SADE includes incidents and near incidents.

13.6 Recording and reporting of AEs and device events

Adverse Event (AE) information will be collected throughout the study and reported to the study coordinator on an Adverse Event Form. This Adverse Event form should be sent to the study coordinator. Contact details are given on page 1. All Adverse Events, regardless of relatedness or outcome, must be reported.

Information reported on the Adverse Event Form shall include a description of the event, the date of event onset, the relatedness of the event to the procedure, the relatedness of the event to the device, actions taken as a result of the event, the outcome of the event, and the date the event was first noticed by the investigator.

For Adverse Events that require immediate reporting (see table 1), initial reporting may be done by e-mail, or on the CRF completed as much as information is available, followed by the completed original adverse event form.

All other AE's must be reported in a timely manner.

